6.6.2. Recommended Duvelisib Dose Modifications for the Management of Duvelisib Toxicities

The dose level of duvelisib may be modified to manage duvelisib toxicities ([Table 12](#)) or overlapping toxicities in combination with pembrolizumab ([Table 10](#)).

Non-hematologic and hematologic AEs for duvelisib for non-overlapping toxicities in combination with pembrolizumab should be managed with supportive care, treatment hold, dose reduction, or discontinuation of duvelisib as described in [Table 12](#). Additional information regarding management of duvelisib toxicities can be found in the Summary of Data and Guidance to the Investigator section of the duvelisib IB.

Refer to [Table 11](#) for dose level modifications recommended for duvelisib. Subjects who have a duvelisib dose reduction due to a toxicity will not be eligible for a dose re-escalation.

Any subject who develops an unacceptable toxicity at the 15 mg BID dosage of duvelisib should discontinue the study interventions.

Duvelisib may be held up to 42 days due to toxicity. While duvelisib is being held, the subject may continue to receive pembrolizumab at the discretion of the Investigator. Doses held for > 42 days due to treatment-related toxicity will result in permanent discontinuation of duvelisib.

If duvelisib is discontinued, the subject will also discontinue pembrolizumab and proceed with their End of Treatment (EoT) Visit.

Table 11: Duvelisib Dose Level Modifications for Toxicities

Dose Level	Duvelisib
Starting Dose	25 mg BID PO
-1	15 mg BID PO ^a

Abbreviations: BID: twice daily; PO: oral.

^a Discontinue duvelisib if subject is unable to tolerate duvelisib 15 mg BID.

Table 12: Recommended Duvelisib Dose Modifications for the Management of Duvelisib Toxicities

Toxicity	Adverse Reaction Grade	Dose Modification and Recommended Management
Non-hematologic Adverse Reactions		
Infections	Grade 3 or higher infection	
 Withhold duvelisib until resolved Resume at the same or reduced dose (see Table 11)
	Clinical CMV infection or viremia (positive PCR or antigen test)	
 Withhold duvelisib until resolved Resume at the same or reduced dose (see Table 11) If duvelisib is resumed, monitor subjects for CMV reactivation (by PCR or antigen test) at least monthly
	PJP	
 For suspected PJP, withhold duvelisib until evaluated

Toxicity	Adverse Reaction Grade	Dose Modification and Recommended Management
		
 For confirmed PJP, discontinue duvelisib
Hematologic Adverse Reactions		
Febrile neutropenia	Grade 3-4	
 Interrupt duvelisib until afebrile and resolution of Grade 3 or Grade 4 neutropenia to Grade ≤ 2 (ANC > 1.0 Gi/L) Monitor ANC at least weekly until > 1.0 Gi/L Resume at same dose (first occurrence) or at a reduced dose for subsequent occurrence
Neutropenia	ANC 0.5 to 1.0 Gi/L	
 Maintain duvelisib dose Monitor ANC at least weekly
	ANC less than 0.5 Gi/L	
 Withhold duvelisib. Monitor ANC until > 0.5 Gi/L Resume duvelisib at same dose (first occurrence) or at a reduced dose for subsequent occurrence (see Table 11)
Thrombocytopenia	Platelet count 25 to < 50 Gi/L (Grade 3) with Grade 1 bleeding	
 No change in dose Monitor platelet counts at least weekly
	Platelet count 25 to < 50 Gi/L (Grade 3) with Grade 2 bleeding or Platelet count < 25 Gi/L (Grade 4)	
 Withhold duvelisib Monitor platelet counts until ≥ 25 Gi/L and resolution of bleeding (if applicable) Resume duvelisib at same dose (first occurrence) or resume at a reduced dose for subsequent occurrence (see Table 11)

Toxicity	Adverse Reaction Grade	Dose Modification and Recommended Management
Non-hematologic Adverse Reactions During the Duvelisib Monotherapy Lead-in Only^a		
Non-infectious Diarrhea or colitis	Mild/moderate diarrhea (Grade 1-2, up to 6 stools per day over baseline) and responsive to antidiarrheal agents, OR Asymptomatic (Grade 1) colitis	
 • No change in dose • Initiate supportive therapy with antidiarrheal agents as appropriate • Monitor at least weekly until resolved
	Mild/moderate diarrhea (Grade 1-2, up to 6 stools per day over baseline) and unresponsive to antidiarrheal agents	
 • Withhold duvelisib until resolved • Initiate supportive therapy with enteric acting steroids (e.g., budesonide) • Monitor at least weekly until resolved • Resume at a reduced dose (see Table 11)
	Abdominal pain, stool with mucus or blood, change in bowel habits, peritoneal signs, OR Severe diarrhea (Grade 3, > 6 stools per day over baseline)	
 • Withhold duvelisib until resolved • Initiate supportive therapy with enteric acting steroids (e.g., budesonide) or systemic steroids • Monitor at least weekly until resolved • Resume at a reduced dose (see Table 11) • For recurrent Grade 3 diarrhea or recurrent colitis of any grade, discontinue duvelisib
	Life-threatening	
 • Discontinue duvelisib
Cutaneous reactions	Grade 1-2	
 • No change in dose • Initiate supportive care with emollients, anti-histamines (for pruritus), or topical steroids • Monitor closely
	Grade 3	
 • Withhold duvelisib until resolved • Initiate supportive care with emollients, anti-histamines (for pruritus), or topical steroids • Monitor at least weekly until resolved • Resume at a reduced dose (see Table 11) • If severe cutaneous reaction does not improve, worsens, or recurs, discontinue duvelisib
	Life-threatening	
 • Discontinue duvelisib
	SJS, TEN, DRESS (any grade)	
 • Discontinue duvelisib
Pneumonitis without suspected infectious cause	Moderate (Grade 2) symptomatic pneumonitis	
 • Withhold duvelisib • Treat with systemic steroid therapy • If pneumonitis recovers to Grade 0 or 1, duvelisib may be resumed at reduced dose (see Table 11) • If non-infectious pneumonitis recurs or subject does not respond to steroid therapy, discontinue duvelisib
	Severe (Grade 3) or life-threatening pneumonitis	
 • Discontinue duvelisib • Treat with systemic steroid therapy

Toxicity	Adverse Reaction Grade	Dose Modification and Recommended Management
ALT/AST elevation	3 to 5 × ULN (Grade 2)	
 Maintain duvelisib dose Monitor at least weekly until return to < 3 × ULN
	> 5 to 20 × ULN (Grade 3)	
 Withhold duvelisib and monitor at least weekly until return to < 3 × ULN Resume duvelisib at same dose (first occurrence) or at a reduced dose for subsequent occurrence (see Table 11)
	> 20 × ULN (Grade 4)	
 Discontinue duvelisib

Abbreviations: ALT: alanine aminotransferase; ANC: absolute neutrophil count; AST: aspartate transaminase; CMV: cytomegalovirus; DRESS: drug reaction with eosinophilia and systemic symptoms; PCR: polymerase chain reaction; PJP: *Pneumocystis jiroveci* pneumonia; SJS: Stevens Johnson syndrome; TEN: toxic epidermal necrolysis; ULN: upper limit of normal.

^a See [Table 10](#) for recommended dose modifications for the management of overlapping toxicities for duvelisib in combination with pembrolizumab.

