 - Total bilirubin level $\leq 1.5 \times$ ULN (exception: subjects with Gilbert's Syndrome may have a bilirubin level $> 1.5 \times$ ULN)
 - AST/serum glutamic-oxaloacetic transaminase (SGOT) and ALT/serum pyruvic transaminase (SGPT) levels $\leq 2.5 \times$ ULN or $\leq 5 \times$ ULN in subjects with liver metastases
- 10. Must have international ratio (INR) or prothrombin time (PT) and activated partial thromboplastin time (aPTT) $\leq 1.5 \times$ ULN, unless subject is receiving anticoagulant therapy in which case PT or aPTT must be within therapeutic range of intended use of anticoagulants
- 11. Must have an Eastern Cooperative Oncology Group (ECOG) performance status ≤ 1
- 12. For male and female subjects of reproductive potential (i.e., not surgically sterile or female subjects who are not postmenopausal), must be willing to use a highly effective method of contraception (see Section 10.4) for the duration of the study interventions and for at least 4 months after the last dose of study interventions
- 13. Must have a negative serum human chorionic gonadotropin (hCG) pregnancy test result within 7 days before first dose of duvelisib if the subject is a woman of childbearing potential (WCBP) (defined in Section 10.4)
- 14. Must provide signed and dated institutional review board (IRB)/independent ethics committee (IEC)-approved informed consent form (ICF) before any study-specific screening procedures are performed

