6.6. Supportive Care, Dose Modifications, and Management of Toxicities

Supportive care should be provided as clinically indicated. Granulocyte colony stimulating factor may be used according to the American Society of Clinical Oncology (ASCO) guidelines (Smith 2015). Transfusions may be used at any time as clinically indicated and according to ASCO guidelines. Subjects on a stable dose of erythropoietin to treat baseline anemia may continue this therapy at this dose.

General recommendations for the management of overlapping toxicities for duvelisib in combination with pembrolizumab (Section 6.6.1), toxicities for duvelisib (non-overlapping toxicities or as monotherapy) (Section 6.6.2), and toxicities for pembrolizumab (non-overlapping toxicities) (Section 6.6.3) are provided below.

Please refer to the pembrolizumab prescribing information (Keytruda 2019) for additional information regarding management of pembrolizumab toxicities.

Additional information regarding management of duvelisib toxicities can be found in the Summary of Data and Guidance to the Investigator section of the duvelisib IB.

In the event that all study interventions are discontinued, subjects should be followed for AEs (for 30 days after the last dose of last study intervention) and survival as outlined in the SoA ([Table 1](#) and [Table 3](#)).

6.6.1. Recommended Dose Modifications for the Management of Overlapping Toxicities for Duvelisib in Combination with Pembrolizumab

Non-infectious diarrhea or colitis, cutaneous reactions, pneumonitis without suspected infectious cause), and elevations in ALT and AST levels are potential overlapping toxicities for duvelisib with pembrolizumab. Refer to [Table 10](#) for recommended management of these events in subjects being treated with duvelisib in combination with pembrolizumab.

If, during the management of an AE for an individual subject receiving both duvelisib and pembrolizumab, the Investigator suspects that pembrolizumab may be the cause of that event, the Investigator should discuss the case with the Medical Monitor. If an excessive rate of Grade 3 or higher overlapping SAEs is observed, the totality of safety data will be evaluated by the Medical Monitor and the Investigators, and a decision to hold enrollment of subjects may be made (see [Section 4.1](#)).

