For additional information, please refer to the prescribing information for pembrolizumab ([Keytruda 2019](#)) and the Summary of Data and Guidance to the Investigator section of the duvelisib IB.

Table 10: Recommended Dose Modifications for the Management of Overlapping Toxicities for Duvelisib in Combination with Pembrolizumab

Toxicity	Adverse Reaction Grade	During Treatment with Duvelisib in Combination with Pembrolizumab	
		Dose Modification	Recommended Management
Non-infectious Diarrhea or colitis	Grade 1 diarrhea (up to 3 stools per day over baseline) and responsive to antidiarrheal agents, OR Asymptomatic (Grade 1) colitis	
 • No change in pembrolizumab dose • No change in duvelisib dose 	
 • Initiate supportive therapy with antidiarrheal agents as appropriate • Monitor at least weekly until resolved or Grade 0
	Grade 1 diarrhea (up to 3 stools per day over baseline) and unresponsive to antidiarrheal agents	
 • Withhold duvelisib dose • No change in pembrolizumab dose 	
 • Treat with enteric acting steroids (e.g., budesonide) • Monitor at least weekly until resolved • Resume duvelisib at a reduced dose when event resolves (see Table 11)
	Grade 2 diarrhea or colitis	
 • Withhold pembrolizumab and duvelisib 	
 • Administer corticosteroids (initial dose of 1 to 2 mg/kg/day prednisone or equivalent followed by a taper) • Resume in subjects with complete or partial resolution (Grades 0 to 1) after corticosteroid taper
	Abdominal pain, stool with mucus or blood, change in bowel habits, peritoneal signs OR Severe diarrhea or colitis (Grade 3, > 6 stools per day over baseline)	
 • Withhold pembrolizumab and duvelisib 	
 • For Grade 2/Grade 3 colitis, initiate supportive therapy with enteric acting steroids (e.g., budesonide) or systemic steroids (initial dose of 1 to 2 mg/kg/day prednisone or equivalent followed by a taper) • Monitor at least weekly until resolved • Resume pembrolizumab treatment when event resolves • Resume duvelisib at a reduced dose when event resolves (see Table 11) • For recurrent Grade 3 diarrhea or recurrent colitis of any grade, discontinue pembrolizumab and duvelisib
	Life-threatening	
 • Discontinue pembrolizumab and duvelisib 	

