Toxicity	Adverse Reaction Grade	During Treatment with Duvelisib in Combination with Pembrolizumab	
		Dose Modification	Recommended Management
Cutaneous reactions	Grade 1-2	
 No change in dose for pembrolizumab or duvelisib 	
 Initiate supportive care with emollients, anti-histamines (for pruritus), or topical steroids Monitor closely
	Grade 3	
 Withhold duvelisib dose Based on the severity of the adverse reaction, withhold or permanently discontinue pembrolizumab 	
 Initiate supportive care with emollients, antihistamines (for pruritus), or topical steroids Monitor at least weekly until resolved Resume duvelisib at reduced dose when event resolves (see Table 11) If severe cutaneous reaction does not improve, worsens, or recurs, discontinue duvelisib
	Life-threatening	
 Discontinue pembrolizumab and duvelisib 	
	SJS, TEN, DRESS (any grade)	
 Discontinue pembrolizumab and duvelisib 	
Pneumonitis without suspected infectious cause	Moderate (Grade 2) symptomatic pneumonitis	
 Withhold pembrolizumab and duvelisib 	
 Treat with corticosteroids (1 to 2 mg/kg/day prednisone or equivalent, followed by corticosteroid taper) If pneumonitis recovers to Grade 0 or 1, pembrolizumab may be resumed and duvelisib may be resumed at reduced dose (see Table 11) If non-infectious pneumonitis recurs or subject does not respond to steroid therapy, discontinue duvelisib and pembrolizumab
	Recurrent Grade 2 pneumonitis, severe (Grade 3), or life-threatening pneumonitis	
 Discontinue pembrolizumab and duvelisib 	

Toxicity	Adverse Reaction Grade	During Treatment with Duvelisib in Combination with Pembrolizumab	
		Dose Modification	Recommended Management
Hepatotoxicity	AST or ALT > 3 and up to 5 × ULN or total bilirubin > 1.5 and up to 3 × the ULN	
 Withhold pembrolizumab and duvelisib 	
 Treat with corticosteroids (0.5 to 1 mg/kg/day prednisone or equivalent followed by corticosteroid taper) Monitor at least weekly until ALT or AST returns to < 3 × ULN Resume treatment when adverse reaction improves to Grade 0 or 1 after corticosteroid taper

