	In subjects without liver metastases, AST or ALT > 5 × ULN or total bilirubin > 3 × ULN	
 Discontinue pembrolizumab and duvelisib 	
	In subjects with liver metastasis and Grade 2 AST or ALT at baseline, with an increase in AST or ALT of 50% or more relative to baseline that persists for at least 1 week	
 Discontinue pembrolizumab and duvelisib 	

Abbreviations: ALT: alanine aminotransferase; AST: aspartate transaminase; DRESS: drug reaction with eosinophilia and systemic symptoms; SJS: Stevens Johnson syndrome; TEN: toxic epidermal necrolysis; ULN: upper limit of normal.

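### Table 10's hepatic rows make no exception for the raised baseline values that criterion 9c admits, and no general sentence bars the first pembrolizumab infusion while a Table 10 hold or stop condition is present

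*Combined protocol and SAP*

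**What the plan says.** **Eligibility.** Section 5.1, criterion 9c, sets AST/ALT at no more than 2.5 x ULN, or 5 x "ULN in subjects with liver metastases". Bilirubin may be up to 1.5 x ULN; subjects with Gilbert's syndrome may exceed this and no upper limit is given.

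**Table 10 (Section 6.6.1).** It gives recommended management "in subjects being treated with duvelisib in combination with pembrolizumab". Its hepatic rows are:
- Withhold both drugs and give corticosteroids: "AST or ALT > 3 and up to 5 × ULN or total bilirubin > 1.5 and up to 3 × the ULN". The management column adds "Monitor at least weekly until ALT or AST returns to < 3 × ULN", with treatment resumed at Grade 0 or 1 after the steroid taper.
- Discontinue both drugs: "In subjects without liver metastases, AST or ALT > 5 × ULN or total bilirubin > 3 × ULN".
- Discontinue both drugs: "In subjects with liver metastasis and Grade 2 AST or ALT at baseline", if AST or ALT then rises by half or more over baseline and stays there for a week.

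**Table 12 (Section 6.6.2).** Its diarrhea/colitis, cutaneous, pneumonitis and ALT/AST rows stand under "Non-hematologic Adverse Reactions During the Duvelisib Monotherapy Lead-in Only" and instruct on duvelisib only. There is no bilirubin row. Its infection and hematologic rows are not limited to the lead-in.

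**First infusion.** Sections 4.1, 6.1.2 and 6.7 and Table 1 give the timing (Cycle 1 Day 8, window ± 5 days), the order relative to the biopsy, and Medical Monitor consultation on dosing adjustments after a delay. None gives a toxicity grade.

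**The concern.** There are two gaps, and they are separate.

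First, a withhold row with no reference to baseline, set beside an eligibility rule that admits values inside that row, tells a site to hold both drugs and start steroids in a subject whose liver tests have not changed. Steroids at that point also work against an immunotherapy. This can arise at any infusion, so it concerns Stage 2 Cycle 1 Day 1 as much as Stage 1 Cycle 1 Day 8.

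Second, a Stage 1 subject may reach Cycle 1 Day 8 with an overlapping toxicity that began on duvelisib alone. Table 12 tells the site what to do with duvelisib and is silent on pembrolizumab. A site could give the first infusion at a value for which Table 10 would at once withhold or stop both drugs. Another site might apply Table 10 before the infusion and wait. Chemistry is scheduled on Day 8, so the question can arise on the day of dosing.

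**Working it through.** The plan states no figure on this point, so there is none to reproduce. The check sets the thresholds side by side.

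**Step 1. Criterion 9c against Table 10 (multiples of ULN).**

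| Group | Allowed at entry (9c) | Table 10 row met with no change |
|---|---|---|
| Liver metastases | AST/ALT up to 5 | Withhold, if above 3 |
| Gilbert's syndrome | Bilirubin above 1.5, no ceiling | Withhold, if up to 3; discontinue, if above 3 without liver metastases |
| All others | AST/ALT up to 2.5; bilirubin up to 1.5 | None |

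Exactly two eligible groups overlap.

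**Step 2. Liver metastases, baseline AST/ALT 4 x ULN.**
- Withhold row: 3 < 4 ≤ 5, so it is met at entry.
- Release: the value must fall below 3 x ULN, that is by more than (4 − 3)/4 = 25% from its entry level. Table 12 labels 3 to 5 x ULN as Grade 2, so Grade 0 or 1 cannot be reached at the entry value.
- Last row of Table 10: discontinue at 1.5 × 4 = 6 x ULN, if sustained for a week.

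For a baseline just above 3, that last threshold is 1.5 × 3 = 4.5 x ULN; for a baseline of 5 it is 1.5 × 5 = 7.5 x ULN. The last row therefore expects these subjects to be on treatment and judges them against their own baseline. The withhold row does not.

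**Step 3. Gilbert's syndrome.** The bilirubin criterion in Section 6.7.1 replaces 2 x ULN by 2 x baseline for these subjects. With an illustrative baseline of 2 x ULN, that is 2 × 2 = 4 x ULN, while Table 10 already withholds both drugs at 2 x ULN. With an illustrative baseline of 3.2 x ULN and no liver metastases, Table 10 says discontinue at entry.

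**Step 4. The same finding before and after the first infusion.**

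| Finding | Table 12, lead-in | Table 10, combination |
|---|---|---|
| Grade 2 diarrhea responsive to antidiarrheals | No dose change | "Grade 2 diarrhea or colitis": withhold both, corticosteroids |
| Grade 2 diarrhea not responsive | Hold duvelisib, enteric steroids, resume at a reduced dose | Same row: withhold both, corticosteroids |
| Grade 2 pneumonitis | Hold duvelisib | Withhold both |
| ALT/AST 3 to 5 x ULN | Maintain duvelisib | Withhold both, corticosteroids |
| ALT/AST above 5 to 20 x ULN, no liver metastases | Hold duvelisib | Discontinue both |
| Bilirubin above 1.5 x ULN | No row | Withhold both; discontinue both above 3 x ULN without liver metastases |

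**Step 5. Is there a start condition elsewhere?** Three rules come near.
- Section 6.6.2 stops pembrolizumab if duvelisib is discontinued.
- Section 6.6.2 leaves continuing pembrolizumab during a duvelisib hold to the Investigator, without a grade.
- Section 6.7.2 requires recovery to baseline or Grade 1 before re-treatment, but only after a DLT.

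None covers a lead-in toxicity that is neither a DLT nor a cause of duvelisib discontinuation.

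**The case against.** The best defence is that Table 10 manages adverse reactions and is not an eligibility screen. Its rows are recommendations, and Section 8.4.1 says that anticipated fluctuations of pre-existing conditions need not count as adverse events. A stable entry value is then arguably outside the table, and a sensible Investigator or Medical Monitor would treat the subject. That is a fair account of the intent and it limits the seriousness. It does not repair the row, which gives a bare threshold while the row for liver metastases in the same table is tied to baseline.

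It can also be said that the pembrolizumab prescribing information and the Investigator's Brochure give further guidance. Neither is available here, so the gap is shown for the protocol text only.

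A reader might infer more in two ways.
- *That the protocol does not say which table governs an event carried across the first infusion.* It does: the word limiting Table 12's rows to the lead-in, the footnote to those rows, and the scope sentence of Section 6.6.1 together point to Table 10 once combination treatment begins. What is missing is the condition for giving that infusion.
- *That the gap makes DLT counts or DLT-evaluability unreliable.* The documents do not support this. Table 12 assigns no DLT status. Section 6.7.1 has its own criteria, requires at least a possible relation to duvelisib, and allows documented case review in both directions. Any shortfall in duvelisib doses would come from Table 12's own hold, not from the boundary between the tables, and replacement under Section 5.6 is optional.

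**Conclusion.** Both gaps stand, as minor points of wording with a safety purpose. Table 10's hepatic withhold and bilirubin discontinue rows lack a baseline exception for the two groups that criterion 9c admits, in Stage 1 and Stage 2, against the intent shown by the table's last row and by Section 6.7.1. Table 12's lead-in rows leave the first pembrolizumab infusion without a general toxicity condition.

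The size cannot be put as a number of subjects: the documents give no frequency for liver metastases with Grade 2 AST/ALT, for Gilbert's syndrome, or for lead-in toxicities present on Day 8. A subject who never receives pembrolizumab is outside the mITT set (Section 9.3), the denominator for ORR, but nothing in the documents shows that this would happen to any number of subjects. The finding assumes the rows are applied as printed.

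**What to change.** 1. Add to Table 10's hepatic rows, for every infusion in both stages: *In subjects with liver metastases and Grade 2 AST/ALT at baseline, AST/ALT that has not risen 50% or more over baseline, and in subjects with Gilbert's syndrome, bilirubin not > 2 x baseline, is not a withhold or discontinue condition.*
2. Add to Table 12's lead-in rows: *The first pembrolizumab infusion is delayed, with Medical Monitor consultation, while a Table 10 withhold or discontinue condition (with the exception above) is present.*

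Both limits come from the protocol: 50% from Table 10's last row, 2 x baseline from Section 6.7.1. A limit of no rise at all over baseline would be too strict, since a move from 4.0 to 4.1 x ULN would then hold treatment that Table 10's last row tolerates up to 6 x ULN.

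The cost is two sentences and some delayed first infusions; design, sample size and DLT definition do not change. Two details need a clinical decision. Because 9c sets no bilirubin ceiling in Gilbert's syndrome, a baseline of 3.2 x ULN would be tolerated up to 2 × 3.2 = 6.4 x ULN. For liver-metastasis baselines above 5/1.5 = 3.33 x ULN, a 50% rise lands above 5 x ULN, where Table 10 already names no action during the first week; the withhold instruction should be stated to apply there too.
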